7.1. Disposition of Patients/Participants and Withdrawals

Disposition will include tabulations of the number of participants randomized into each treatment group, the number of participants completing the study, and the number of participants withdrawing, along with the reasons for withdrawal, by treatment group and overall within each study part.

A listing will be presented to describe whether the subject completed the study, date of completion or early withdrawal, and the reason for discontinuation, if applicable. A listing will be provided to describe the date when informed consent was obtained and if the subject meets all inclusion/exclusion criteria.

7.2. Protocol Violations and Deviations

Protocol deviations will be identified and classified as important or non-important for statistical analysis purposes before unblinding. Important protocol deviations will be used to exclude participants from the PP population.

The protocol deviation data with the verbatim description, the date of deviation and whether the deviation is classified as minor or major will be listed.

7.3. Demographics and Other Baseline Characteristics

These analyses will be conducted for the Safety and ITT populations and will be presented by treatment group and study part.

Demographics will include age, sex, race, ethnicity, height, weight, and BMI. Baseline subject characteristics will include medical history and disease characteristics.

For the continuous variables, the number of non-missing values and the mean, standard deviation, minimum, median and maximum will be tabulated. For the categorical variables, the counts and proportions of each value will be tabulated. These summaries will be performed for the safety population overall, and by treatment.

The number and percent of participants reporting various medical histories will be grouped by MedDRA system organ class and preferred term (coded using MedDRA v24.0).

Medical history details as collected on the CRF such as verbatim description, dictionary terms, onset date, and stop date will be presented as a subject data listing.

7.4. Exposure and Compliance

IP exposure and dosing information including the number of doses and amount of IP received will be listed for each subject.

8. Efficacy Analysis

Efficacy data for Part 1 participants will be listed only, except for data from Part 1 participants that are included in the Combined Population.

For Part 2 and the Combined Population, all statistical testing for endpoints will be 2-sided and will be evaluated in an exploratory manner to inform decisions about future trials. Tests comparing treatment and control group will report point estimates, p-values, and 95% confidence intervals. In Part 2 and the Combined Population, all efficacy variables will be summarized descriptively. The primary analytic method will include adjustment for *a priori* selected covariates as described in [Section 6.1.2](#).

8.1. Primary Efficacy Analysis

The primary efficacy endpoint is the proportion of participants alive and free of respiratory failure at Day 28.

The proportion of respiratory failure-free surviving participants in each Part 2 treatment group at Day 28 will be analyzed using logistic regression with treatment as a factor and age, diabetes, body mass index, and baseline sPLA2 activity included as covariates. Dummy/reference coding will be used in all logistic regression implementations. The risk difference between varespladib and placebo along with the 95% CI and p-value will be presented. Note that logistic regression typically involves calculation and testing of odds ratios, however, this analysis will focus on presenting and testing the risk difference via the delta method ([Ge et al, 2011](#)).

The ITT, PP and Combined populations will be used to analyze the primary efficacy endpoint. The ITT population will be the primary population for the efficacy analyses.

8.1.1. Sensitivity Analyses of the Primary and Key Secondary Efficacy Endpoints

Two types of sensitivity analyses will be conducted for the primary efficacy endpoint and key secondary efficacy endpoints using the ITT population. The following sensitivity analysis will be conducted in Part 2 subjects only.

One sensitivity analysis will be to examine the effect of covariate selection. This work will include estimating (1) the effect of treatment on the outcome adjusted for only the *a priori* specified model covariates (see section 6.2.1), and (2) and if significant imbalance is observed in other important covariates, then adjustment for the *a priori* specified covariates as well as other variables that are imbalanced between the treatment arms.

A second sensitivity analysis will be stratified estimates of the effect of treatment. The following strata will be examined: 1) high or low sPLA2 activity, with high defined as the median sPLA2 value or greater, 2) male or female gender, 3) high or low SpO2 at baseline dichotomized based on median value; 4) baseline WHO ordinal scale score dichotomized based on the median value; and 5) use of remdesivir or dexamethasone at baseline. Stratified estimates for a given variable will not be conducted if the number of patients within a stratum are insufficient to support the analysis.

Sensitivity analyses are exploratory and will be interpreted as evidence to inform additional research. The above listed sensitivity analyses will be applied to the primary efficacy endpoint and the following key secondary endpoints: days of oxygen support through day 28, ICU days through day 28, 9-point WHO clinical status scale, and mortality through Day 60.

8.2. Secondary Efficacy Analysis

The secondary efficacy endpoints are:

- Clinical improvement, as measured by the World Health Organization (WHO) 9-point ordinal scale through Day 60
- Time to and proportion of participants with all-cause mortality through Day 60
- Proportion of participants who experienced respiratory failure within the first 28 days after randomization
- Among patients that never experience respiratory failure in the first 28 days, time to initiation, duration, and proportion of subjects receiving supplemental oxygen or other respiratory support within the first 28 days after randomization
- Among patients that experience respiratory failure in the first 28 days, time to initiation and duration of the forms of respiratory support meeting criteria outlined in critical COVID criteria (exclusion criteria 1.c.i) within the first 28 days after randomization
- Number of days of oxygen support through Day 28 after randomization
- SpO2 through Day 28 after randomization
- Number of ventilator-free days through Day 28 after randomization
- Number of hospitalization days through Day 28 after randomization
- Number of days without renal stabilization and/or replacement through Day 28 after randomization
- Number of organ failure-free days through Day 28 after randomization
- Number of days at elevated level of care (ICU) through Day 28 after randomization
- Number of healthcare encounters through Day 28 after randomization.

The ITT and Combined populations will be used to analyze the secondary efficacy endpoints. The ITT population will be considered to be the primary population for the efficacy analyses.

8.2.1. World Health Organization (WHO) 9-point Ordinal Scale

The investigators will assess participants' clinical status using the WHO 9-point ordinal scale:

| Patient State | Descriptor | Score |
|------------------------------|--|-------|
| Uninfected | No clinical or virological evidence of infection | 0 |
| Ambulatory | No limitations on activities | 1 |
| | Limitation on activities | 2 |
| Hospitalized; mild disease | No oxygen therapy | 3 |
| | Oxygen by mask or nasal prongs | 4 |
| Hospitalized; severe disease | Noninvasive ventilation or high-flow oxygen | 5 |
| | Intubation and mechanical ventilation | 6 |
| | Ventilation plus additional organ support (pressors, renal replacement therapy (RRT), extracorporeal membrane oxygenation (ECMO) | 7 |
| Dead | Death | 8 |

Descriptive summaries of observed values and changes from baseline in the WHO 9-point scale will be presented for each scheduled visit within treatment group. Distribution of outcomes on the WHO ordinal scale will also be described via plots in supplemental analyses.

Mean change from baseline in the WHO 9-point scale for each assessment will be analyzed using ANCOVA at each scheduled post-baseline visit. The model will include treatment, age, diabetes, body mass index, and baseline value as covariates. The least squares (LS) mean change from baseline will be presented along with the associated 95% CI within each treatment group. In comparing treatments, LS mean differences in change from baseline between treatments will be presented along with associated 95% CIs and p-values. Participants that die will have a score of 8 assigned to all scheduled visits on and after the date of death.

8.2.2. All-Cause Mortality

All-cause mortality from randomization through Day 60 will be analyzed using a Cox-Proportional hazard model. The number of participants who experience the event and rate ratio with 95% CI will be presented. The p-value to test if the rate ratio between treatments differs from 1 will be evaluated. Kaplan-Meier methodology will be used to estimate the median time to the event and 95% CI. Time to all-cause mortality will be calculated according to [Section 6.1.7](#).

Censoring events include loss to follow-up prior to Day 60. Covariates will include those a priori specified in [Section 6.1.2](#), and Efron's method for handling tied time-to-events will be used. The p-value testing for non-zero treatment effect will be obtained from a Wald chi-square test, and

the 95% CI associated with the treatment effect will be a Wald-type CI.

Additionally, the proportion of participants who die will be analyzed using the same logistic regression and risk difference method with dummy coding as the primary endpoint (Ge et al, 2011). In general, the proportions of participants with an event on or before Day 60 will be analyzed.

8.2.3 Proportion of participants who experienced respiratory failure within the first 28 days after randomization

The proportion of participants experiencing respiratory failure from randomization through Day 28 will be analyzed using the same logistic regression and risk difference method with dummy coding as the primary endpoint. Respiratory failure is defined as defined by requiring HFNC >20 L/min, non-invasive positive pressure ventilation, mechanical ventilation, or ECMO, or clinical diagnosis of respiratory failure (exclusion criteria 1.c.i) at any time during the 28 days after randomization. Note that those who experience mortality after respiratory failure are still counted towards this analysis. Those who experience mortality without prior respiratory failure will not be counted towards this analysis.

8.2.4 Among patients that do not experience respiratory failure in the first 28 days, time to initiation and duration of supplemental oxygen or other respiratory support within the first 28 days

The number of days of supplemental oxygen or other respiratory support in patients not meeting the criteria for respiratory failure from randomization through Day 28 will be summarized descriptively and analyzed using ANCOVA. The LS means will be presented along with the associated 95% CI within each treatment group. In comparing treatments, LS mean differences between treatments will be presented along with associated 95% CIs and p-values. For Part 1 analysis, this endpoint will be reported in all patients in the ITT population.

The time to start of supplemental oxygen or other respiratory support from randomization through Day 28 will be analyzed using a Cox-Proportional hazard model. The number of participants who experience the event and rate ratio with 95% CI will be presented. The p-value to test if the rate ratio between treatments differs from 1 will be evaluated. Kaplan-Meier methodology will be used to estimate the median time to the event and 95% CI. Censoring events include loss to follow-up prior to Day 28. Mortality will not be considered a censoring event and instead will be analyzed as if this patient was on supplemental oxygen or other respiratory support for all days between randomization and Day 28. If mortality or the event of interest does not occur, all subjects will be censored at Day 28. Covariates will include those a priori specified in [Section 6.1.2](#), and Efron's method for handling tied time-to-events will be used. The p-value testing for non-zero treatment effect will be obtained from a Wald chi-square test, and the 95% CI associated with the treatment effect will be a Wald-type CI.

Duration and time to supplemental oxygen or other respiratory support through Day 28 will be calculated according to [Section 6.1.7](#)

8.2.5. Among patients that experience respiratory failure in the first 28 days, time to initiation and duration of the forms of respiratory support meeting criteria outlined in critical COVID criteria (exclusion criteria 1.c.i) within the first 28 days

The number of days of respiratory support meeting criteria outlined in the critical COVID criteria among patients that experience respiratory failure in the first 28 days from randomization through Day 28 will be summarized descriptively and analyzed using ANCOVA. The LS means will be presented along with the associated 95% CI within each treatment group. In comparing treatments, LS mean differences between treatments will be presented along with associated 95% CIs and p-values.

For study Part 1 analysis, this endpoint will be reported in all patients in the ITT population.

The time to start of respiratory support through Day 28 will be analyzed using a Cox-Proportional hazard model. The number of participants who experience the event and rate ratio with 95% CI will be presented. The p-value to test if the rate ratio between treatments differs from 1 will be evaluated. Kaplan-Meier methodology will be used to estimate the median time to the event and 95% CI. Censoring events include loss to follow-up prior to Day 28. Mortality will not be considered a censoring event and instead will be analyzed as if the patient was on the forms of supplemental oxygen for all days between randomization and Day 28. If mortality or the event of interest does not occur, all subjects will be censored at Day 28. Covariates will include those a priori specified in [Section 6.1.2](#), and Efron's method for handling tied time-to-events will be used. The p-value testing for non-zero treatment effect will be obtained from a Wald chi-square test, and the 95% CI associated with the treatment effect will be a Wald-type CI.

Duration and time to the forms of respiratory support through Day 28 will be calculated according to [Section 6.1.7](#).

In order to assign the worst total score for death, participants that die will have all days from randomization through Day 28 treated as if they were receiving critical COVID-level respiratory support (i.e., analyzed as having 28 days of COVID-level respiratory support) for these analyses. Participants that do not die but have missing data will not be excluded from the analysis of duration or time-to-event endpoints and will have an appropriate value assigned.

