3.2. Sample Size and Power

Approximately 90 evaluable participants are planned for this study. Eighteen participants will be randomized into Part 1 of the study in a 5:5:5:3 ratio with 3 varespladib arms and a placebo arm. In Part 2 of the study, 72 participants will be randomized in a 1:1 ratio with the selected varespladib arm from Part 1 of the study and a placebo arm. No stratification variables will be used.

This is a pilot study and exploratory in nature. The sample size is not based on a formal power calculation.

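### SAP 8.2.2: the Wald p-value and CI for the Cox mortality rate ratio become uninformative if one arm has no deaths, and then conflict with the risk difference planned for the same deaths

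*SAP*

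**What the plan says.** SAP 8.2.2 states: "All-cause mortality from randomization through Day 60 will be analyzed using a Cox-Proportional hazard model". The null is a rate ratio of 1. The test is fixed ("The p-value testing for non-zero treatment effect will be obtained from a Wald chi-square test"), as is the interval ("the 95% CI associated with the treatment effect will be a Wald-type CI"). For ties, "Efron's method for handling tied time-to-events will be used". The covariates, from SAP 6.1.2, are diabetes, age, body mass index and baseline sPLA2 activity. No other Cox test or interval is named for an arm with few or no deaths. Protocol 13.1.4.3 asks for a Cox p-value but does not name the test, so this is a choice made in the SAP.

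The last paragraph of 8.2.2 adds a second analysis of the same deaths: the proportion dying by Day 60, by logistic regression with a delta-method risk difference.

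On size, SAP 3.2 says "In Part 2 of the study, 72 participants will be randomized in a 1:1 ratio" and "The sample size is not based on a formal power calculation". The opening of SAP Section 8 says that for Part 2 and the Combined Population "all statistical testing for endpoints will be 2-sided and will be evaluated in an exploratory manner". SAP 8.1.1 lists mortality among the key secondary endpoints ("9-point WHO clinical status scale, and mortality through Day 60"). SAP Section 10 records that recruitment was paused with one Part 2 participant, that Part 1 will carry no efficacy p-values, and that an amendment will follow for Part 2 reporting of the endpoints in 8.2.4 and 8.2.5.

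**The concern.** A Wald test divides the estimate by a standard error computed at the estimate. If one arm has no deaths, the Cox log rate ratio has no finite maximum. The iterations drive it towards minus infinity, its standard error grows faster than the estimate, and the Wald statistic falls to zero. The test therefore gives its weakest result in the data most favourable to one arm. Score (log-rank type) and likelihood-ratio tests do not take their variance from the diverged estimate, and do not fail in this way.

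At stake is the rate ratio for a key secondary endpoint in a trial meant to inform later ones. Its CI could carry no information, and its p-value could contradict the risk difference reported in the same section.

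**Working it through.** The documents give no power figure or expected death rate to reproduce. All death counts and rates below are assumptions.

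**Inputs.** 72 participants at 1:1, so 36 v 36 (SAP 3.2). Cox model, Efron ties, Wald test and CI (SAP 8.2.2). Four covariates (SAP 6.1.2). Censoring at Day 60 (SAP 6.1.7).

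**Step 1: 0 v 7 deaths, no covariates, distinct death times.** Just before death j (j = 0 to 6) the risk set holds 36 varespladib and 36 − j placebo participants. With b the log rate ratio:

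- Log partial likelihood: −Σ log(36 − j + 36e^b). It rises without limit in −b, so there is no finite estimate.
- Information for large negative b: about e^b × Σ 36/(36 − j) = 7.66 e^b. Hence SE ≈ e^(−b/2)/√7.66, and |Wald z| ≈ |b| √7.66 e^(b/2), which tends to 0.
- Stopping on a relative gradient of 1e-8: b = −17.30, SE = 2,060, z = 0.0084, p = 0.993.
- Stopping on a relative log-likelihood change of 1e-9: b = −20.30, SE = 9,232, z = 0.0022, p = 0.998.
- Wald 95% CI for the rate ratio: 0 to infinity.
- Likelihood ratio: 2 Σ log[(72 − j)/(36 − j)] = 2 × 5.173 = 10.35, p = 0.0013.
- Score: U = Σ 36/(72 − j) = 3.655 in absolute value and V = 1.745, so U²/V = 7.66, p = 0.0057.
- Firth fit: rate ratio 0.06, profile-likelihood 95% CI 0.0005 to 0.50, p = 0.0047.

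With four simulated covariates (300 data sets) the Wald p ranged from 0.993 to 0.999. In a Combined Population of 41 v 39 (36 + 5 and 36 + 3), 0 v 7 gives 0.993.

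**Step 2: other counts, 36 v 36, no covariates.**

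| Deaths | Wald p | Score p | Likelihood-ratio p |
|---|---|---|---|
| 0 v 3 | 0.996-0.999 | 0.079 | 0.039 |
| 0 v 5 | 0.994-0.999 | 0.021 | 0.007 |
| 0 v 8 | 0.993-0.998 | 0.003 | 0.0005 |
| 1 v 7 | 0.060 | 0.027 | 0.019 |

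More deaths in the other arm do not rescue the Wald test. With one death in the low arm the model fits, but the Wald test is still weak.

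**Step 3: the companion analysis for 0 v 7.** Risk difference = 0 − 7/36 = −19.4 points. SE = √(0.194 × 0.806/36) = 6.6 points. The 95% CI is −32.4 to −6.5 and p = 0.003. An adjusted version with four simulated covariates (40 draws) gave median p = 0.002, maximum 0.005.

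**Step 4: how often an arm has no deaths.** P(no deaths among 36) = (1 − rate)^36: 33% at a 3% death rate, 16% at 5%, 2% at 10%. If varespladib halves the placebo rate, the chance that exactly one arm has none is 43%, 26%, 17% and 6% at placebo rates of 5%, 8%, 10% and 15%.

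**Step 5: power, two-sided 0.05, 36 per arm.** Exponential survival in whole days to Day 60. The Cox model has treatment plus four covariates with modest effects (1,000-1,500 trials per row). Log-rank and risk difference are unadjusted (risk difference 20,000 trials).

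| Deaths, placebo v varespladib | Cox Wald | Log-rank | Risk difference |
|---|---|---|---|
| 20% v 2% | 23% | 76% | 79% |
| 20% v 3% | 25% | 66% | 70% |
| 20% v 5% | 28% | 51% | 53% |
| 15% v 3% | 12% | 44% | 48% |
| 25% v 10% | 31% | 37% | 41% |
| 30% v 10% | 49% | 55% | 60% |

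Repeat runs gave Wald power of 28% and 32% at 20% v 3%, and 23% and 28% at 20% v 5%. At 20% v 3%, 33% of trials had no varespladib deaths. Wald rejected in none of those and log-rank in 94%, so they account for about 0.33 × 94 = 31 of the 41 points lost.

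Rejection under no effect at 10%, 15% and 20% mortality: Wald 2.0%, 3.8%, 4.6%; log-rank 5.6%, 5.3%, 4.7%; plain likelihood ratio 7.3%, 7.1%, 6.4%. Firth likelihood ratio: 5.3% and 5.0% at 15% and 20%.

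**The case against.** The strongest reply is that the same section already holds a working analysis of these deaths. That stands. A reader might infer that a strong survival difference would be reported as none. The documents do not support this: death counts and the risk difference would be printed too, and the risk difference has about the power of the log-rank test. What remains is that the section could print p about 0.003 and p above 0.99 for the same deaths, with no rule for reading them together.

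Four further limits also stand.

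- **8.2.4 and 8.2.5.** They repeat the Wald sentence, and a reader might extend the failure to them. It needs an arm with no events. In 8.2.5 the subset is defined by needing the support being timed. In 8.2.4 the event is oxygen or other support in hospitalised severe COVID-19, where low SpO2 is a qualifying sign and deaths are treated as being on support. A zero-event arm is implausible in either, and no failure is shown.
- **Strata in 8.1.1.** A median split leaves about 18 per arm, so an arm without deaths is likelier. But the SAP drops stratified estimates where patient numbers are too small. That rule counts patients rather than deaths, so it may not catch every case, but it is a safeguard.
- **Size of the loss.** It is not large whenever varespladib mortality is low. At 10% v 5%, Wald power is 4% and likelihood-ratio power 16%; a small effect leaves little power to lose. The large losses need 75-90% fewer deaths on treatment.
- **Exploratory status and the pause.** Tests are exploratory, Part 1 reports no efficacy p-values, and Part 2 had one participant. This limits the present effect. It does not make a CI of 0 to infinity useful, since the SAP reports estimates and CIs to judge clinical importance.

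**Conclusion.** The point holds for the Cox analysis of mortality in SAP 8.2.2. With no deaths in one arm, the prespecified Wald p-value exceeds 0.99 and the CI is unbounded. This follows from the method and needs no assumed rate. The exact value, 0.993 to 0.999, depends on the software's stopping rule and the covariates.

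The power loss does rest on assumed rates: roughly 20 to 40 points against log-rank at 20% v 3-5%, about 5-10 points at 25-30% v 10%, and limited when the effect is small. The practical consequence is an uninformative rate ratio and a p-value that contradicts the risk difference beside it. It arises only if Part 2 or the Combined Population is analysed under 8.2.2. The change is worth making because it is cheap and can precede the Part 2 outcome data.

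**What to change.** In SAP 8.2.2, replace the Wald chi-square test and Wald-type CI with a Firth-penalised partial-likelihood-ratio test of the treatment coefficient and a profile-likelihood 95% CI, from the same covariate-adjusted Cox model with Efron ties. Show the unadjusted log-rank p-value beside it. The Part 2 SAP amendment announced in Section 10 is the place; its stated purpose is the 8.2.4 and 8.2.5 endpoints, so 8.2.2 must be added. The matching sentence in those two subsections may be changed for consistency.

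The cost is one sentence of SAP text. No new data are needed, and there is no conflict with the protocol, which names no test. The downside is slightly lower power than a plain likelihood-ratio test (72% v 79% at 20% v 2%). That test is less suitable because its simulated false-positive rate is about 7%, against about 5% for Firth.

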6.1.7. Derived Variables

- Respiratory failure is defined as the requirement for use of intubation/mechanical ventilation, an oxygen rate with high flow nasal cannula greater than 20 L/min, non-invasive positive pressure respiratory support, or ECMO, or clinical diagnosis of respiratory failure.
- Respiratory failure-free survival is defined as the combination of no respiratory failure (defined above) and no report of mortality from any cause.
- Mortality from any cause is defined as death listed on the Study Completion CRF or WHO 9-point ordinal scale assessment of death.
- Non-invasive positive pressure respiratory support is defined as the use of continuous positive airway pressure (CPAP) or bilevel positive airway pressure (BiPAP).
- Ventilator use is defined as the use of mechanical ventilation, CPAP, or BiPAP.
- Organ failure is defined as a reported AE indicating a ‘failure’ of respiratory, cardiovascular, hepatic, renal, coagulation, or neurological reported at the PT level or

‘insufficiency’ reported as the lowest level term.

- Renal stabilization or replacement is defined as reported use of any type of dialysis in concomitant medications with a route recorded as (“HEMODIALYSIS”, “PERITONEAL DIALYSIS”, or “DIALYSIS”).
- Time to initiation of supplemental oxygen or other respiratory support in the first 28 days after randomization = (the earliest of Day 28 or date/time of the first use – date/time of randomization) + 1.
- Duration of supplemental oxygen or other respiratory support in the first 28 days after randomization = (the earliest of Day 28 of the study or date/time of the last use – the latest of date/time of the first supplemental oxygen or other respiratory support or date/time of randomization) + 1.
- Time to initiation of intubation/mechanical ventilation, an oxygen rate with high flow nasal cannula greater than 20 L/min, non-invasive positive pressure respiratory support, ECMO in the first 28 days after randomization = (the earliest of Day 28 or date/time of the first support – date/time of randomization) + 1.
- Duration of intubation/mechanical ventilation, an oxygen rate with high flow nasal cannula greater than 20 L/min, non-invasive positive pressure respiratory support, or ECMO in the first 28 days after randomization = (the earliest of Day 28 of the study or date/time of the last specified respiratory support – the latest of date/time of the first specified respiratory support or randomization) + 1.

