- For the time till all-cause mortality Cox proportional hazards model, time to all-cause mortality or censoring will be calculated as follows
 - If mortality occurs within 60 days post-randomization; then Time to all-cause mortality or censoring = date/time of death – date/time baseline + 1.
 - If mortality occurs on or after 60 days post-randomization; then Time to all-cause mortality or censoring = 60 days.
 - If mortality does not occur, and last follow-up is prior to 60 days; then Time to all-cause mortality or censoring = date/time of last follow-up – date/time baseline + 1.
 - If mortality does not occur, and last follow-up is on or after 60 days; then Time to all-cause mortality or censoring = 60 days.
- Change from baseline = value at current time point – value at baseline.
- TEAE = any adverse event with an onset or worsening date/time after the date/time of the first administration of IP and prior to the 30 days after last dose of IP.

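### SAP 8.2.4 and 8.2.5 give conflicting censoring rules for a participant lost event-free before Day 28, and the 6.1.7 time-to-initiation formulas cannot censor before Day 28

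*SAP*

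**What the plan says.** SAP 8.2.4 covers time to supplemental oxygen or other support among participants without respiratory failure. SAP 8.2.5 covers time to critical-level support among those with it. Both plan a Cox model with Kaplan-Meier medians, and both state two censoring rules:

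- "Censoring events include loss to follow-up prior to Day 28". No censoring date is given.
- Two sentences later: "If mortality or the event of interest does not occur, all subjects will be censored at Day 28".

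Deaths have their own rule: they are not censored but analysed as if on support for all days from randomization to Day 28.

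Both sections refer to SAP 6.1.7 for the calculation; 8.2.4 says "Duration and time to supplemental oxygen or other respiratory support through Day 28 will be calculated according to" that section. There, time to initiation is ("the earliest of Day 28 or date/time of the first use – date/time of randomization) + 1" for any support, and ("the earliest of Day 28 or date/time of the first support – date/time of randomization) + 1" for critical-level support. The mortality time in the same section has a separate branch that begins "If mortality does not occur, and last follow-up is prior to 60 days" and uses the last follow-up date.

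SAP 6.1.4 adds general rules. Missing data not due to death are derived from contemporaneous clinical data where possible, and otherwise the last observation is carried forward. Participants without an event stay in the analysis with a suitable value, which is not specified.

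SAP 10 says that Part 1 (N=18) will be reported with summary statistics and confidence intervals for secondary outcomes, without tests or P values for efficacy, and that the 8.2.4 and 8.2.5 endpoints will be analysed in the whole Part 1 ITT population.

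**The concern.** A participant lost before Day 28, alive and without the event, falls under both censoring sentences. One implies censoring when contact ends; the other sets Day 28. The formulas do not resolve this in favour of last contact, because they contain no such date. A programmer who follows 6.1.7 will keep the participant in the risk set, event-free, for days on which nobody observed them.

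That inflates the denominator of every later risk set. Cumulative incidence of needing support comes out too low in any arm with losses, and an arm with more losses is flattered relative to the other. Two programmers could also produce different results from the same SAP.

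**Working it through.** **1. The formula applied literally.** Take Day 1 as randomization. With no first use, time = 28 − 1 + 1 = 28, whatever the day of loss. Censoring at last contact on Day L gives L − 1 + 1 = L.

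| Lost event-free on | 6.1.7 value | Last-contact value | Unobserved days credited |
|---|---|---|---|
| Day 2 | 28 | 2 | 26 |
| Day 5 | 28 | 5 | 23 |
| Day 10 | 28 | 10 | 18 |
| Day 14 | 28 | 14 | 14 |
| Day 21 | 28 | 21 | 7 |

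**2. Do the general rules repair this?** No. Carrying the last observation forward keeps an event-free participant event-free to Day 28, and the unspecified value in 6.1.4 names no date. Contemporaneous clinical data help only where records exist after contact is lost.

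**3. Cumulative incidence.** There is no plan figure to reproduce: SAP 3.2 states that there is no formal power calculation, and neither document gives an event or dropout rate. I therefore assume exponential event and dropout times. Let p be the true 28-day incidence and d the dropout by Day 28, with Λ = −ln(1 − p) and Γ = −ln(1 − d). Under the Day 28 rule

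observed incidence = Λ/(Λ + Γ) × [1 − (1 − p)(1 − d)].

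For p = 0.40 and d = 0.10: Λ = 0.511, Γ = 0.105, so 0.511/0.616 × (1 − 0.60 × 0.90) = 0.829 × 0.46 = 0.381. Expected early event-free losses in an arm of 36 (72 randomized 1:1 in Part 2): 36 × 0.171 × 0.46 = 2.8.

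| True incidence | 5% dropout | 10% dropout | 20% dropout |
|---|---|---|---|
| 20% | 19.5% | 19.0% | 18.0% |
| 40% | 39.1% | 38.1% | 36.2% |
| 60% | 58.7% | 57.4% | 54.7% |

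At 40% incidence, about 1.4, 2.8 and 5.7 of 36 are wrongly carried to Day 28. These counts are for a whole arm; the 8.2.4 subset is smaller. Censoring at last contact recovers the true incidence under these assumptions.

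**4. Hazard ratio.** Large-sample Cox simulation (40,000 per arm, Efron ties), with 40% placebo incidence assumed:

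| Dropout, varespladib v placebo | True HR | Last contact | Day 28 rule |
|---|---|---|---|
| 10% v 10% | 1.0 | 0.995 | 0.995 |
| 20% v 5% | 1.0 | 0.992 | 0.907 |
| 5% v 20% | 1.0 | 0.998 | 1.092 |
| 20% v 5% | 0.6 | 0.592 | 0.543 |
| 5% v 20% | 0.6 | 0.602 | 0.660 |

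The shift favours whichever arm loses more participants. With equal loss it vanishes to within simulation error.

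**The case against.** **Administrative censoring.** The Day 28 sentence may be meant only for participants still followed on that day, with the loss-to-follow-up sentence governing everyone else. That is a natural reading and may be what the authors intended. It does not remove the point: the sentence says all subjects, and the only formula supplied cannot return a time before Day 28. The last-follow-up branch for mortality shows that the term was written where it was wanted.

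**Reach.** Part 2 had one participant at the pause, Part 1 efficacy carries no P values, and SAP 10 announces an amendment covering these endpoints, though not censoring specifically. In Part 2 the 8.2.5 subset consists of participants who had respiratory failure, so nearly all have the event and the rule hardly applies. Whether any of the 18 Part 1 participants was lost event-free is unknown. Protocol 10.2 has hospitalized participants assessed daily, and Protocol 9.5.1 separates stopping drug from leaving the study, so heavy early loss is not a given. All of this stands and limits the weight of the point.

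**Stronger readings that the documents do not support.**

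- A reader might infer that duration is also scored too favourably, since that formula ends at "the earliest of Day 28 of the study or date/time of the last use". But SAP 6.1.4 carries the last observation forward, which would extend support for someone last seen on it, and 8.2.5 promises a suitable value for survivors with missing data. The direction is unsettled.
- A reader might measure the Part 1 error as the change in an arm mean when 28 replaces the day of loss. That is not a bias estimate: someone censored on Day 5 has an unknown time beyond Day 5, so 5 is not the true value either. SAP 10 promises means for continuous outcomes and does not say how time-to-event outcomes will be summarised.
- A reader might infer a large distortion by placing all loss in one arm on Day 3. With 10% or 20% lost that way, the hazard ratio falls to about 0.86–0.91 or 0.75–0.79, but nothing in the documents suggests such a pattern. At 10% against 5% spread over 28 days it is about 0.97.

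**Conclusion.** The point holds as a conflict in the censoring rule, combined with formulas that implement the unfavourable side of it. Under the literal formula, cumulative incidence is understated by about 1 to 4 percentage points at an assumed 40% incidence and 5–20% dropout. The hazard ratio is affected only if loss differs between arms: about 0.91 or 1.09 at a true 1.0 for 20% against 5%, depending on which arm loses more.

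These sizes rest on assumed dropout and event rates and exponential times. Last-contact censoring is itself unbiased only if loss is unrelated to prognosis.

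The affected results are 8.2.4 and the unsubsetted Part 1 ITT summaries of both endpoints. All are exploratory. The change should be made because it is cheap, but it does not threaten the trial's primary result.

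**What to change.** - **SAP 8.2.4 and 8.2.5:** replace the Day 28 sentence with: participants without death or the event are censored at the earlier of last contact and Day 28. Keep the stated rule for deaths.
- **SAP 6.1.7:** for both endpoints, define time to initiation as the earliest of first use (or first support), last contact and Day 28, minus randomization, plus 1, with an event/censor flag.
- **Part 1 summary:** report time to initiation by Kaplan-Meier, not as a mean, so that a censored time is never averaged as if it were observed.
- **Timing:** make the change before Part 1 is reported, and carry it into the protocol and SAP amendment announced in SAP 10.

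The cost is a few lines of wording and programming. The last follow-up date is already needed for mortality. The only downside is slightly less nominal follow-up.
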